5.1.2 Exclusion criteria

Patients meeting any of the following exclusion criteria within 4 weeks (unless otherwise stated) of being enrolled are not to be enrolled in the study.

- Component of small-cell cancer or sarcomatoid cancer
- Prior therapy with any systemic infusion or injection therapy (chemotherapy or biologic therapy) within twenty-eight days prior to study entry; greater than or equal to 2 weeks of oral biologic or oral chemotherapy
- Patients must have recovered from toxicities from prior systemic anticancer treatment or local therapies.
- Patients who have undergone major surgery < 4 weeks or minor surgery < 2 weeks prior to registration. Wounds must be completely healed prior to study entry and patients recovered from all toxicities from surgery. Placement of a vascular access device is not considered major or minor surgery in this regard.
- Prior radiation therapy is allowed as long as the irradiated area was not the sole source of measurable disease and radiotherapy was completed with recovery from

toxicity, at least three weeks prior to enrollment. If the irradiated area is the only site of disease, there must be evidence of progressive disease.

- Uncontrolled central nervous system (CNS) metastases (previously treated with radiation and off steroids is acceptable)
- Patient with active or uncontrolled infection.
- Recent or active bleeding diathesis or arterial vascular event within 4 weeks.
- Pregnant or nursing (Fertile patients must use effective contraception during and for up to 3 months after completion of study treatment)
- Patients may not be receiving any other investigational agents.
- Previous assignment to treatment during this study. Subjects permanently withdrawn from study participation will not be allowed to re-enter study.
- Uncontrolled hypertension (systolic pressure >140 mm Hg or diastolic pressure > 90 mm Hg [NCI-CTCAE v4.0] on repeated measurement) despite optimal medical management.
- Active or clinically significant cardiac disease including:
 - Congestive heart failure – New York Heart Association (NYHA) > Class II (section 13.4).
 - Active coronary artery disease.
 - Cardiac arrhythmias requiring anti-arrhythmic therapy other than beta blockers or digoxin.
 - Unstable angina (angina symptoms at rest), new-onset angina within 3 months before consenting or myocardial infarction within 6 months before consenting.
- Evidence or history of bleeding diathesis or coagulopathy.
- Any hemorrhage or bleeding event \geq NCI CTCAE Grade 3 within 4 weeks prior to start of study medication.
- Arterial or venous thrombotic or embolic events such as cerebrovascular accident (including transient ischemic attacks), deep vein thrombosis or pulmonary embolism **within 6 month before the start of study medication** (except for adequately treated catheter-related venous thrombosis occurring more than one month before the start of study medication)
- Subjects with thrombotic, embolic, venous, or arterial events, such as cerebrovascular accident (including transient ischemic attacks) deep vein thrombosis or pulmonary embolism within 6 months of start of study treatment within 6 months of informed consent.
- Subjects with any previously untreated or concurrent cancer that is distinct in primary site or histology from breast cancer except cervical cancer in-situ, treated localized basal cell carcinoma, Gleason score ≥ 6 prostate cancer or superficial bladder tumor. Subjects surviving a cancer that was curatively treated and without evidence of disease for more than 3 years before registration are allowed. All cancer treatments for another malignancy must be completed at least 3 years prior to study entry (i.e., signature date of the informed consent form).
- Patients with pheochromocytoma.
- Known history of human immunodeficiency virus (HIV) infection or current chronic or active hepatitis B or C infection requiring treatment with antiviral therapy.
- Ongoing infection $>$ Grade 2 NCI-CTCAE v4.0.
- Symptomatic metastatic brain or meningeal tumors.
- Presence of a non-healing wound, non-healing ulcer, or bone fracture.
- Renal failure requiring hemo- or peritoneal dialysis.
- Dehydration Grade ≥ 1 NCI-CTCAE v4.0.
- Patients with seizure disorder requiring medication.
- Persistent proteinuria \geq Grade 3 NCI-CTCAE v4.0 (> 3.5 g/24 hrs, measured by urine protein:creatinine ratio on a random urine sample).
- Interstitial lung disease with ongoing signs and symptoms at the time of informed consent.

- Pleural effusion or ascites that causes respiratory compromise (\geq NCI-CTCAE version 4.0 Grade 2 dyspnea).
- History of organ allograft (including corneal transplant).
- Known or suspected allergy or hypersensitivity to any of the study drugs, study drug classes, or excipients of the formulations given during the course of this trial.
- Any malabsorption condition.
- Women who are pregnant or breast-feeding.
- Any condition which, in the investigator's opinion, makes the subject unsuitable for trial participation.
- Substance abuse, medical, psychological or social conditions that may interfere with the subject's participation in the study or evaluation of the study results.

5.1.3 Excluded therapies and medications, previous and concomitant

- Concurrent anti-cancer therapy (chemotherapy, radiation therapy, surgery, immunotherapy, biologic therapy, or tumor embolization) other than study treatment (Regorafenib, other agents being investigated in combination with Regorafenib).
- Prior use of Regorafenib.
- Concurrent use of another investigational drug or device therapy (i.e., outside of study treatment) during, or within 2 weeks of trial entry (signing of the informed consent form).
- Major surgical procedure, open biopsy, or significant traumatic injury within 28 days before start of study medication.
- Patients being treated with anticoagulant will be allowed to participate provided no prior evidence of an underlying abnormality in these parameters exists. For anticoagulants that require monitoring, standards should be considered and controlled by the investigator. For NOACS an individual risk benefit in accordance with the applicable labels and/or local guidelines should be carefully assessed

Use of any herbal remedy (e.g. St. John's Wort [Hypericum perforatum])

5.1.4 Selection of study population

General Guidelines

Eligible patients will be entered on study at the following institutions: the Kirklin Clinic, UAB, Birmingham, AL; Wayne State University Karmanos Cancer Institute, Detroit, MI; (UAB research nurse to be designated by [name], Director of UAB Oncology Clinical Trials, Clinical Studies Unit (CSU), UAB). All sites should call the Study Coordinator to verify agent availability. Following registration, patients should begin protocol treatment within 72 hours. Issues that would cause treatment delays should be discussed with the Principal Investigator. If a patient does not receive protocol therapy following registration, the patient's registration on the study may

be cancelled. The Study Coordinator should be notified of cancellations as soon as possible.

Registration Process

The Clinical Trials Network Monitoring Office (CTNMO) of the UAB Comprehensive Cancer Center (CCC) coordinates investigator-initiated clinical trials under Good Clinical Practice conditions at participating sites to achieve timely study subject enrolment. Once a study subject has been screened and deemed eligible for study entry by the participating site, a study-specific study subject eligibility checklist, a copy of the dated and signed consent form, and corresponding source documentation are faxed to the participating site study coordinator for eligibility verification. Subsequently, a study-specific number is assigned to the study subject and sent to the participating site. Finally, a Patient Registration Form is completed and faxed by the CTNMO site to the participating study coordinator. Queries regarding data accuracy are forwarded from the participating site coordinator to the CTNMO site for clarification or correction. Once the CTNMO site addresses queries, any corrected data forms or copies of corrected source documentation are faxed to the participating site study coordinator.

5.2 Withdrawal of subjects from study

5.2.1 Withdrawal

Subjects **must be withdrawn from the trial** (treatment and procedures) for the following reasons:

- Subject withdraws consent from study treatment and study procedures. A subject must be removed from the trial at his/her own request or at the request of his/her legally acceptable representative. At any time during the trial and without giving reasons, a subject may decline to participate further. The subject will not suffer any disadvantage as a result.
- Pregnancy. Pregnancy will be reported as an SAE. (Note: subjects who have been withdrawn from treatment with study drug because of pregnancy should not undergo CT scans [with contrast]/MRI or bone scans while pregnant.)
- If, in the investigator's opinion, continuation of the trial would be harmful to the subject's well-being.
- Subject is lost to follow-up.
- Death.

Subjects **may be withdrawn from the study** for the following reasons:

- The subject is non-compliant with study drug, trial procedures, or both; including the use of anti-cancer therapy not prescribed by the study protocol.
- Severe allergic reaction to Regorafenib (such as exfoliative erythroderma or Grade 3 or 4 hypersensitivity reaction).
- The development of a second cancer.
- Development of an intercurrent illness or situation which would, in the judgment of the investigator, significantly affect assessments of clinical status and trial endpoints.
- Deterioration of ECOG performance status to 4.

- Use of illicit drugs or other substances that may, in the opinion of the investigator, have a reasonable chance of contributing to toxicity or otherwise skewing trial result.

Any subject removed from the trial will remain under medical supervision until discharge or transfer is medically acceptable.

In all cases, the reason for withdrawal must be recorded in the CRF and in the subject's medical records.

Details for the premature termination of the study as a whole (or components thereof [e.g. centers, treatment arms, dose steps]) are provided in Section 10 (Premature termination of the study).

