2.2 Secondary Objectives

- Measurable disease response rate (RECIST)
- Overall survival
- Comparison of observed PFS6 with expected/estimated PFS6 by nomogram
- Toxicities

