7.1.2 Long term follow up

After study drug treatment ends patients will be evaluated 4 weeks after last dose to assess toxicities and then per investigator discretion using good clinical practice up to study closure to acquire information on survival.

Telephone follow-up is acceptable.

In case of difficulty in contacting a patient during follow up, every attempt should be made to reconnect with the patient or, if it is thought that a patient may have died, to establish a date of death. Patients who withdraw consent from study drug treatment shall enter the long-term follow-up period unless consent to follow-up is specifically withdrawn.

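### Sections 5.2.1 and 7.1.2 conflict on whether patients withdrawn for harm, ECOG 4, allergy or similar reasons stay in outcome follow-up, so overall survival can be informatively censored

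*Combined protocol and SAP*

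**What the plan says.** Section 5.2.1 has two lists and no category for stopping drug while remaining in follow-up.

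- The mandatory list is withdrawal from the trial, with the scope spelled out in brackets as "treatment and procedures) for the following reasons". Beside withdrawn consent, pregnancy, loss to follow-up and death, it contains this reason: "If, in the investigator's opinion, continuation of the trial would be harmful to the subject's well-being".
- The permissive list says that subjects "may be withdrawn from the study". It includes non-compliance, second cancer, intercurrent illness, "Severe allergic reaction to Regorafenib (such as exfoliative erythroderma or Grade 3 or 4 hypersensitivity reaction" and "Deterioration of ECOG performance status to 4".

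For a subject who has been removed, 5.2.1 promises only medical supervision until discharge or transfer. It mentions neither survival nor progression follow-up.

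Section 7.1.2 starts from a different event, the end of study drug: "After study drug treatment ends patients will be evaluated 4 weeks after last dose to assess toxicities". Further contact, to learn survival status, is at the investigator's discretion until study closure. Telephone contact is acceptable, and sites must make every attempt to establish a date of death. The one sentence saying that patients shall enter long-term follow-up is about those who withdraw consent from study drug.

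Section 2.2 lists "Overall survival" as a secondary objective. Section 8 gives no estimator and no censoring rule for it.

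**The concern.** Stopping a drug and ceasing to be observed are different events. Harm, a severe allergic reaction or a fall to ECOG 4 may be a reason for the first; none is in itself a reason for the second. If withdrawal for these reasons also ends outcome collection, the patients who disappear are partly those closest to death. A Kaplan-Meier analysis assumes that censored patients have the same outlook as those still at risk. When they are censored because they are deteriorating, their deaths drop out and survival is overstated. The same patients would contribute no later progression date.

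Other sections blur the same line. Section 5.2.2 defines a dropout by discontinuing study participation. Section 5.2.3 treats any dropout as in effect replaced by the surplus enrolment. Section 6.5 lets a subject be discontinued from the trial for non-compliance with study drug.

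**Working it through.** **1. The plan's own figure.** Section 8.3 states 79.6% power for PFS6 of 5% against 20% with 32 evaluable patients and a cut-off of five. The exact binomial gives P(X ≥ 5 | n = 32, p = 0.20) = 0.7956 and P(X ≥ 5 | n = 32, p = 0.05) = 0.0204. The figure reproduces, and this point does not change it. No power, sample size or threshold is stated for overall survival.

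**2. The passages side by side.**

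| Reason | Status in 5.2.1 | Scope in 5.2.1 | Follow-up stated in 5.2.1 |
|---|---|---|---|
| Investigator-judged harm | mandatory | treatment and procedures | no |
| ECOG 4 | permissive | the study | no |
| Severe allergy | permissive | the study | no |
| Intercurrent illness | permissive | the study | no |
| Second cancer, non-compliance | permissive | the study | no |

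Section 7.1.2 is not limited by the reason for stopping drug, so it can be read as covering all of these. It does not say that it applies to someone withdrawn from the trial. One site could end follow-up under 5.2.1 while another continues it under 7.1.2, each with text to point to.

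**3. Size if follow-up is lost (illustration).** The input from the documents is the historical median survival of 6 to 9 months in Section 1.1.1, midpoint 7.5. The assumptions are exponential survival, and a share q of patients censored L = 1 month before death with the death never recorded.

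Let λ = ln 2 / 7.5 = 0.0924 per month. At time t the proportion still at risk is (1 − q)e^(−λt) + q·e^(−λ(t+L)), and deaths are observed at rate (1 − q)λe^(−λt). The ratio is a constant hazard, so

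estimated median = 7.5 × [(1 − q) + q·e^(−λL)] / (1 − q), with e^(−0.0924) = 0.912.

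- q = 0: 7.5 months
- q = 10%: 7.5 × 0.9912 / 0.9 = 8.3 months
- q = 20%: 7.5 × 0.9824 / 0.8 = 9.2 months
- q = 30%: 7.5 × 0.9736 / 0.7 = 10.4 months

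Twelve-month survival is 0.5^(12/median): 33% when q = 0, then 37%, 41% and 45% (0.365, 0.405 and 0.450).

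Simulated trials of 35 patients with 12 months of accrual and a cut-off at 18 months agree. The median rises from 7.6 to 8.2, 9.2 and 10.0 months, and 12-month survival from 33% to 37%, 41% and 45%. The simulated median at 30% is below the formula because some trials of this size do not reach a median by the cut-off. With a true median of 6 months the formula gives 6.6, 7.3 and 8.3; with 9 months it gives 9.9, 11.1 and 12.6.

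**4. A longer lag.** With L = 3 months, e^(−0.277) = 0.758. At q = 20% the estimate is 7.5 × (0.8 + 0.1516) / 0.8 = 8.9 months. The bias shrinks but does not vanish.

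**The case against.** A reader might infer that the plan withdraws patients for all these reasons and that overall survival is therefore informatively censored. The documents do not support that.

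- ECOG 4, allergy and intercurrent illness are permissive criteria. Of the drug-stopping reasons discussed here, only harm is mandatory. The pregnancy note within the mandatory list speaks of withdrawal from study drug, so even that list partly means stopping treatment.
- Section 7.1.2 directs survival follow-up and death tracing after drug ends, without regard to the reason. Its sentence on withdrawn consent is better read as extending follow-up to a doubtful group than as limiting it.
- The reporting table in 7.4.1.4.1 explains that later unrelated deaths need no serious-event report because death is an endpoint followed separately.
- Note G to the schedule in 7.1 exempts only death, withdrawn consent and loss to follow-up from the end-of-treatment evaluation. Section 7.4.3 requires any death within 30 days of that visit to be reported. A death one month after stopping drug would usually fall inside that window, so the one-month scenario needs both 7.1.2 and safety reporting to fail.
- For PFS6, Section 4 counts clinical progression as an event, and the decision rule counts patients who remain progression-free. A patient with unknown status is not naturally a success.

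All of this stands, and it turns an asserted bias into a possible one. It does not remove the conflict. Safety reporting covers only early deaths, later contacts are discretionary, and 5.2.1 still tells a site that a harmed patient leaves procedures as well as treatment.

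**Conclusion.** The point holds as a conflict between two sections, with a possible rather than an established bias. Applied literally, 5.2.1 can end survival and progression follow-up for reasons related to prognosis, and the resulting error in overall survival would be upward. Applied to everyone, 7.1.2 brings the survival bias to zero.

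The 8.2 to 10 month range shows only how sensitive a 35-patient estimate would be. The withdrawn share, the lag before death, the exponential form and the cut-off are all assumptions, and nothing in the documents predicts a 10% to 30% loss. Overall survival is secondary and unpowered, and the rule of five in 32 is untouched. Because Section 8 has no censoring rule that would settle the matter at analysis, the text should be corrected.

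**What to change.** Reconcile the two sections.

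1. In 5.2.1, keep every listed reason as it is. State that those concerning harm, pregnancy, allergy, illness, second cancer, non-compliance, performance status and substance use end study drug only. These patients continue survival follow-up under 7.1.2 and progression follow-up under the 7.1 schedule, with the existing imaging restriction in pregnancy.
2. State that only withdrawal of consent to follow-up, loss to follow-up or death ends study participation.
3. In 7.1.2, extend the rule on entering long-term follow-up to every patient who stops drug for any reason, and give a contact interval in place of pure discretion.
4. Align the dropout definition in 5.2.2 and the non-compliance sentence in 6.5.
5. In Section 8, say that overall survival is censored at the date last known alive.

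The cost is protocol wording and a few survival contacts, by telephone if need be, that 7.1.2 already foresees. No rule on when to stop drug changes.

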5.2.2 Screen Failures/Dropouts

A subject who discontinues study participation prematurely for any reason is defined as a "dropout" if the subject has already been randomized, assigned to treatment/run-in/wash-out, and administered at least one dose of study drug.

A subject who, for any reason (e.g. failure to satisfy the selection criteria), terminates the study before the time point used for the definition of "dropout" (see above) is regarded a "screening failure".

5.2.3 Replacement

No withdrawn subjects will be replaced. The study will enroll 35 patients out of which 32 will be evaluable for end point analysis. Any drop out will effectively be replaced through the nature of design.

6. Treatment[s]

6.1 Treatments to be administered

This is a single arm study in which all patients will receive Regorafenib orally. Patients will visit the clinic on the first day of each cycle for assessments for responses and safety. Instructions about medications will be given to the patient as mentioned in sections 6.3.1.

6.2 Treatment assignment

6.2.1 Regorafenib

Regorafenib tablets will be packaged in high density polyethylene bottles with a white child resistant closure and induction seal. Each bottle includes 30 tablets (for randomized studies) or 28 tablets (for open-label studies) and a 3-gram desiccant. The bottles will have a label affixed containing study identification, product identification, and quantity of tablets. Once the drug has been received it must be kept in a secure, dry location. Study drug must be stored in its original bottle at a temperature not above 25°C (77°F).

The study drug must be exclusively used for the investigation specified in this protocol and it will only be accessible to authorized staff.

6.3 Blinding

This is a non-randomized study and hence investigators, study staff and patients will know about the treatment being administered. There will no blinding of any involved personnel or participants.

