Historical pooled PFS6 is approximately 20% for previously used agents. In this study, those progressing within 6 months of prior therapy will be enrolled with the goal of detecting PFS6 in $\geq 20\%$ of patients, while PFS6 in <5% will be considered to be of poor interest. Selecting patients following 1-3 prior regimens and within 6 months of prior therapy will ensure timely accrual of a homogeneous population and enrich for patients unlikely to attain PFS6 without active therapy. Thus, outcome results will be more interpretable, given these stipulations. Tumor tissue will be collected to be studied retrospectively to analyze genomics/proteomics to identify an association with PFS6.

Nanostring platform for gene expression analysis of formalin-fixed paraffin embedded tumor

Gene expressing profiling performed by the nanostring technology, which utilizes formalin-fixed paraffin embedded (FFPE) tissue using the nCounter® appears highly promising (59). This technology provides robust data from FFPE tissue using the nCounter® GX Kit and offers high levels of precision and sensitivity (>1 copy per cell) without the need for amplification of ≥ 100 ng of RNA. Nanostring is a multiplexed (up to 800 genes per reaction) platform, which utilizes digital counting and excellent quantitative reproducibility by employing two ~50 base probes per mRNA that hybridize in solution. Multiple successful applications utilizing the nCounter System to subtype tumors, formulate tumor prognostic signatures, or discover novel targets for therapy have been reported in other malignancies (60-63). Notably, the 50-gene PAM50 signature (Prosigna™) derived from nanostring was approved by the US FDA in 2013 to assess the risk of distant recurrence at 10 years in postmenopausal women with hormone receptor-positive breast cancer. Indeed, the PAM50 gene score, which is enriched for proliferation-associated genes appeared more robust than the Oncotype DX® recurrence score in predicting recurrence (62). Gene expression by nanostring may be proposed for a highly relevant panel of 797 genes including 230 human cancer-promoting genes, 519 kinase genes, 32 bladder cancer specific genes recently reported by TCGA including 4 genes involved in epigenetic regulation, 85 DNA damage repair genes, 3 stem cell relevant genes and 8 internal reference genes (64).

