7.2.2 Exploratory tumor tissue studies and central pathology review

Twenty archival formalin-fixed paraffin-embedded (FFPE) tumor slides will be requested for potential central pathology review and molecular studies. Fifteen slides of 10 μM thickness sections each and 5 slides of 5 μM thickness sections each will be requested from all institutions. In the event of attainment of the primary endpoint (i.e. PFS6 in $\geq 20\%$ of patients), slides will be obtained and following central pathology review for determining histologic subtype, tumor will be demarcated from adjacent normal tissue on the H+E slide to guide procurement of tumor-enriched samples. The 10 μM sections will be used for RNA isolation toward gene expression profiling for ~ 800 cancer-promoting, kinase, DNA-damage repair, bladder cancer-specific and stem cell panel genes by the nanostring platform performed centrally in the UAB Comprehensive Cancer Center. A total surface area of tumor 100 mm^2 is adequate to harvest the necessary amount of RNA (100 ng) using the RNAeasy Mini Kit (Qiagen), and the quality of the RNA will be assessed via the 260/280 ratio using nanodrop. [name] at UAB Radiation Oncology Dept. will perform the nanostring studies as described in previous publications utilizing the nCounter by inputting RNA directly into a hybridization reaction containing color-coded molecular barcodes representing the genes of interest [56]. Immunohistochemistry (IHC) is performed on the 5 μM section slides for VEGFR2 and Tie2 by previously described methods using appropriate controls.

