8.3 Statistical and analytical plans

The primary endpoint of the study is the rate of progression free survival (PFS) at 6 months (PFS6). Given the poor prognosis of this patient population and data from other studies of salvage therapy, a PFS6 of $\geq 20\%$ is felt to be important for this regimen, while a PFS6 $< 5\%$ is felt to be of poor interest. The trial also enrolls patients who progress within 6 months of last cycle of prior chemotherapy to enhance the interpretability of outcomes, since such patients are unlikely biologically to be progression-free for 6 more months without active therapy that favorably impacts on tumor biology to extend PFS. SAS version 9.3 was used to calculate power. The justification for the proposed sample size is based on an exact test for a binomial proportion with a one-sided significance level of 5%. With 32 evaluable subjects,

we will have approximately 80% power (79.6%) to reject the null hypothesis that PFS6 is < 5% in favor of PFS6 \geq 20%. Given that 5-10% of patients may be inevaluable, up to 35 patients may be enrolled. If five or more patients remain progression-free at 6 months, this regimen will be considered to be of significant interest.

Chi-square or Fisher's exact test will be employed to determine univariate association of biomarker status with PFS6 and objective response. Descriptive statistics including frequencies and proportions will be calculated to summarize safety and toxicity outcomes. Specifically, the number of adverse events (AE) and serious adverse events (SAE) will be tabulated and summarized. Point estimates and exact binomial (Clopper-Pearson) confidence intervals (CI) will be calculated to estimate the incidence of AEs and SAEs. The precision of these estimates, i.e., width of the confidence interval, will depend on the estimated incidence of each outcome. The table below gives the exact 95% confidence intervals for a range of incidences, assuming 32 evaluable subjects.

Number of subjects experiencing event	Estimated Incidence	95% Exact CI for Incidence		Width of CI
		Lower Limit	Upper Limit	
1	0.031	0.001	0.162	0.161
2	0.062	0.008	0.208	0.200
4	0.125	0.035	0.290	0.255
8	0.250	0.115	0.434	0.319
16	0.500	0.319	0.681	0.362

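### Tie2 and VEGFR2 staining is scored after PFS6 is known, with no masking of the reader and no cut-off fixed beforehand, so the exploratory association is exposed to outcome-aware scoring

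*Combined protocol and SAP*

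**What the plan says.** Section 7.2.2 makes the tissue work conditional on the trial result: "In the event of attainment of the primary endpoint", which it describes as PFS6 in at least 20% of patients, slides are obtained and reviewed. Immunohistochemistry is then done "for VEGFR2 and Tie2 by previously described methods using appropriate controls". The assessment schedule in Section 7.1 places the request for archival slides at screening, but not their reading. Section 1.2 is consistent with late reading: "Tumor tissue will be collected to be studied retrospectively to analyze genomics/proteomics to identify an association with PFS6".

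Section 2.3 lists the association of Tie2 and VEGFR2 staining with PFS as exploratory. Section 7.2.1 says this work may be performed. Section 8.3 names chi-square or Fisher's exact test to "determine univariate association of biomarker status with PFS6 and objective response".

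On masking, the only text is Section 6.3. Its first sentence gives the reason: "This is a non-randomized study and hence investigators, study staff and patients will know about the treatment being administered". The second is unqualified: "There will no blinding of any involved personnel or participants".

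The documents give no scoring scale, positivity cut-off, number of readers, slide coding or masking to outcome for the staining.

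**The concern.** In a one-arm trial, knowing the treatment cannot distort a comparison between marker-positive and marker-negative patients, because everyone receives the same drug. Knowing the outcome can. Staining intensity is a visual judgment, and the test needs a positive/negative status for which no rule is given. By the time slides are read, PFS6 has been determined. If the reader can see who was progression-free, borderline slides may be called in the expected direction. If the cut-off is chosen after scores and outcomes are side by side, the same result can arise without misreading a single slide.

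The protocol supplies an expectation, since Sections 1.1.2 and 1.2 present TIE2 and VEGFR inhibition as a likely route to benefit. With about 32 patients and few successes, a handful of calls can decide whether a marker appears associated with PFS6, and nobody could later tell a scoring artefact from a real signal. What is at stake is the credibility of that exploratory finding, not the efficacy conclusion.

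**Working it through.** **Design inputs.** Section 8.3 gives 32 evaluable patients, a null PFS6 of 5%, an alternative of 20%, and interest declared at 5 or more successes. The exact binomial tail gives P(X ≥ 5 | n = 32, p = 0.20) = 0.7956, which reproduces the stated 79.6%. The actual one-sided alpha is P(X ≥ 5 | n = 32, p = 0.05) = 0.0204. No stated figure is in dispute; this only confirms the inputs.

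**Number of successes.** The tissue trigger in Section 7.2.2 is PFS6 of at least 20%. Since 6/32 = 18.75% and 7/32 = 21.9%, 7 is the first count that meets it, leaving 25 failures. Section 8.3 declares interest at 5/32 = 15.6%, so 5 is also run, and 10 as a higher case.

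**How few slides matter.** Assume about half the patients are truly marker-positive with no association. The p-values are from the two-sided Fisher test.

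| Scores changed | Positive among PFS6 successes | Positive among failures | p |
|---|---|---|---|
| None | 4/7 | 12/25 | 1.00 |
| 2 in each group | 6/7 | 10/25 | 0.083 |
| 3 successes only | 7/7 | 12/25 | 0.025 |
| 3 in each group | 7/7 | 9/25 | 0.007 |

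The third row can be checked by hand. With 19 positives among 32, P(7 of 7) = C(19,7)/C(32,7) = 50,388/3,365,856 = 0.0150. The less likely tables in the other tail add C(13,7)/C(32,7) = 0.0005 and 19 × C(13,6)/C(32,7) = 0.0097, for a total of 0.025.

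**False-positive rate.** Let π be the true marker prevalence, the same in both outcome groups, and e the probability that a score discordant with the expectation (negative in a success, positive in a failure) is shifted toward it. Then

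- P(scored positive | success) = π + (1 − π)e
- P(scored positive | failure) = π(1 − e)

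For π = 0.50 and e = 0.20 these are 0.60 and 0.40. For π = 0.35 and e = 0.20 they are 0.48 and 0.28. Summing the two binomial probabilities over every table with two-sided Fisher p ≤ 0.05, with 7 successes and 25 failures:

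| e | π = 0.50 | π = 0.35 |
|---|---|---|
| 0 | 2.5% | 2.5% |
| 0.10 | 4.3% | 5.9% |
| 0.20 | 10.4% | 14.1% |
| 0.30 | 22.5% | 28.4% |

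At e = 0.20, 5 successes give 8.4% (π = 0.50) and 10.4% (π = 0.35); 10 successes give 11.8% and 14.2%. The pattern does not depend on the choice of 7.

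Only the 32 patients and the 20% trigger come from the documents. The values of e, the values of π and the direction of shift are assumptions. Objective response was not calculated separately.

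**The case against.** The strongest reply is that Section 6.3 belongs to the treatment chapter and explains itself by knowledge of treatment. A reader might infer from its last sentence that outcome masking of the laboratory is ruled out. The documents do not support that: the sentence completes a statement about an open-label drug, and coded slides would not contradict it. This part of the reply stands. The gap lies in Sections 7.2.2 and 8.3, and Section 6.3 only adds unqualified wording that points the wrong way.

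A reader might also infer that histology review biases a planned association. No test of histologic subtype against PFS6 or response is planned. In Section 7.2.2 subtype is determined at central review, before tumor is marked off from normal tissue to guide sampling. That inference should not be drawn.

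Third, the trigger is a trial-level result. That the trial met its endpoint does not show that the reader sees each patient's outcome, and the documents neither grant nor deny that access. The previously described staining methods, which cannot be seen here, may include a scoring rule. Both points stand, and they make this an uncontrolled risk rather than a shown bias.

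Fourth, the analysis is exploratory and contingent, the objective states no direction, and at a 10% shift the rate is still close to the nominal 5%. This is also true and keeps the severity low. It does not remove the gap: the plan as written contains no safeguard, and one costs almost nothing.

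**Conclusion.** The point holds as a low-severity, inexpensive improvement. Followed as written, the plan allows Tie2 and VEGFR2 staining to be scored, and its positivity cut-off chosen, after PFS6 is known and without masking, before status is tested against PFS6 and response. The size depends on how far scores would shift, which the documents cannot tell us. Under the stated assumptions the false-positive rate per marker goes from 2.5% to 4-6% with a 10% shift, 10-14% with 20% and 22-28% with 30%. The primary PFS6 test, its 79.6% power and the safety analyses are unaffected.

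**What to change.** In Section 7.2.2, state that archival slides are labelled with a study code, and that Tie2 and VEGFR2 scoring and the positivity cut-off are completed and locked without access to PFS6, response or survival data. The statistician links the locked file to outcome only afterwards, for the test in Section 8.3. In Section 6.3, limit the statement to treatment, for example: Treatment is open-label.

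The cost is a few sentences of protocol text, coded labels and one locked score file. Readers, slides, assays and sample size stay the same. Because reading already comes last in the sequence, the step does not alter the conduct of the trial.
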